## Statistical Analysis Plan Template

Sponsor:	ProQR Therapeutics		
Protocol:	PQ-110-002		
Document Version No.:	1.0	Document Date:	04 JAN 2022

- from logMAR 2 (if only clinical assessment result available) to a logMAR value of < 1.7 based on ETDRS
- from logMAR 1.7-2 (based on BRT) to a logMAR value of < 1.7 based on ETDRS AND the BCVA change from baseline is equal or better than -0.3 logMAR (ie,  $\leq$  -0.3 logMAR)

### 4.8.1.3. Vision Preservation Analysis for the First Treated Eyes

A vision preservation analysis will be summarized on overall group and performed on the first treated eyes which were treated in PQ-110-001 and continue to be treated in PQ-110-002 with the following definitions of achieving the vision preservation:

- BCVA change from baseline for on-chart subjects (ie, BCVA < 1.7 logMAR based on ETDRS):
  - Among the subjects that are responders at month 12 to the -0.3 criterion
    - Remain responders at -0.3 logMAR
    - Remain responders at -0.2 logMAR (allowing a worsening of + 0.1 log MAR)
    - Have a worsening of equal or more than + 0.2 log MAR
    - Have a worsening of equal or more than + 0.3 log MAR
  - Among the subjects that are responders at month 12 to the -0.2 criterion
    - Remain responders at -0.2 logMAR
    - Have a worsening of equal or more than + 0.1 log MAR
    - Have a worsening of equal or more than + 0.2 log MAR
    - Have a worsening of equal or more than + 0.3 log MAR

## Statistical Analysis Plan Template

Sponsor:	ProQR Therapeutics		
Protocol:	PQ-110-002		
Document Version No.:	1.0	Document Date:	04 JAN 2022

- BCVA change from baseline for off-chart subjects (ie, BCVA  $\geq 1.7$  logMAR based on BVRT/clinical practice assessment): leading to a categorical change in VA category according to Holladay VA reference scale (Section 8) or Lange VA reference scale (Section 9)
  - Among the subjects that are responders at month 12 to the responder criterion defined in the section 4.8.1.2, the same rule used for on-chart subjects will be performed.

### 4.8.2. **Mobility Course**

## Statistical Analysis Plan Template

Sponsor:	ProQR Therapeutics		
Protocol:	PQ-110-002		
Document Version No.:	1.0	Document Date:	04 JAN 2022

## Statistical Analysis Plan Template

Sponsor:	ProQR Therapeutics		
Protocol:	PQ-110-002		
Document Version No.:	1.0	Document Date:	04 JAN 2022

## Statistical Analysis Plan Template

Sponsor:	ProQR Therapeutics		
Protocol:	PQ-110-002		
Document Version No.:	1.0	Document Date:	04 JAN 2022

## Statistical Analysis Plan Template

Sponsor:	ProQR Therapeutics		
Protocol:	PQ-110-002		
Document Version No.:	1.0	Document Date:	04 JAN 2022

### 4.8.3. Full-Field Stimulus Threshold Testing (FST)

Full field stimulus testing captures threshold measurements for each stimulus (blue and red light).

Measurements with a Fail value of “0” are successful, and any measurements with a Fail value of “1” are unsuccessful. If the threshold value fails, the next successful value will be captured. FST thresholds will be measured by an independent reading center according to the schedule of events in section 2.4 and the Imaging Charter.

The mean FST values (i.e., light sensitivity) for each eye (first treated eye, treated and non-treated contralateral eye) will be summarized using continuous descriptive statistics by treatment group, eye and visit for each stimulus color, for all subjects in the Efficacy Evaluable Population. The FST values are the average of all FST stimulus sizes (in log cd/m^2) for the given eye at a given visit and stimulus color.

Descriptive statistics will be based on only successful thresholds ('acceptable data').

A responder analysis will be performed on the contralateral eyes treated in PQ-110-002 with the following definitions of responders:

- Blue FST change from baseline:
  - Equal or better than -0.7 log (cd/ m^2), smaller values are better
  - Equal or better than -0.5 log (cd/ m^2), smaller values are better
- Red FST change from baseline:

## Statistical Analysis Plan Template

Sponsor:	ProQR Therapeutics		
Protocol:	PQ-110-002		
Document Version No.:	1.0	Document Date:	04 JAN 2022

- Equal or better than  $-0.7 \log(cd/m^2)$ , smaller values are better
- Equal or better than  $-0.5 \log(cd/m^2)$ , smaller values are better

A vision preservation analysis for FST will be performed the first treated eyes which were treated in PQ-110-001 and continue to be treated in PQ-110-002 with the following definitions of achieving the vision preservation:

- Blue FST change from baseline:
  - Among the subjects that are responders at month 12 to the  $-0.7$  criterion
    - Remain responders at  $-0.7 \log(cd/m^2)$
    - Remain responders at  $-0.6 \log(cd/m^2)$  (allowing a worsening of  $+ 0.1 \log(cd/m^2)$ )
    - Remain responders at  $-0.5 \log(cd/m^2)$  (allowing a worsening of  $+ 0.2 \log(cd/m^2)$ )
    - Have a worsening of equal or more than  $+ 0.3 \log(cd/m^2)$
  - Among the subjects that are responders at month 12 to the  $-0.5$  criterion
    - Remain responders at  $-0.5 \log(cd/m^2)$
    - Have a worsening of equal or more than  $+ 0.1 \log(cd/m^2)$
    - Have a worsening of equal or more than  $+ 0.2 \log(cd/m^2)$
    - Have a worsening of equal or more than  $+ 0.3 \log(cd/m^2)$
- Red FST change from baseline:
  - Among the subjects that are responders at month 12 to the  $-0.7$  criterion
    - Remain responders at  $-0.7 \log(cd/m^2)$
    - Remain responders at  $-0.6 \log(cd/m^2)$  (allowing a worsening of  $+ 0.1 \log(cd/m^2)$ )
    - Remain responders at  $-0.5 \log(cd/m^2)$  (allowing a worsening of  $+ 0.2 \log(cd/m^2)$ )

## Statistical Analysis Plan Template

Sponsor:	ProQR Therapeutics		
Protocol:	PQ-110-002		
Document Version No.:	1.0	Document Date:	04 JAN 2022

- Have a worsening of equal or more than  $+ 0.3 \log (\text{cd/ m}^2)$
- Among the subjects that are responders at month 12 to the -0.5 criterion
  - Remain responders at  $-0.5 \log (\text{cd/ m}^2)$
  - Have a worsening of equal or more than  $+ 0.1 \log (\text{cd/ m}^2)$
  - Have a worsening of equal or more than  $+ 0.2 \log (\text{cd/ m}^2)$
  - Have a worsening of equal or more than  $+ 0.3 \log (\text{cd/ m}^2)$

In addition, tables with individual values over time will also be produced, for both original and change from baseline values. A subject listing of all failed and successful threshold FST, including FST related comments will be produced for the Efficacy Evaluable Population.

### 4.8.4. Optical Coherence Testing

OCT parameters related to EZ line/width are considered efficacy parameters and are presented in the current section. These OCT values will be summarized by treatment group, eye and visit for the Efficacy Evaluable Population using continuous descriptive statistics. OCT data and any comments that may be relevant to the OCT grading will be listed for each subject in the Efficacy Evaluable Population. The measures listed below, regardless of confidence score (high confidence, adequate confidence, inadequate confidence) will be used for summaries and listings.

The following continuous data are considered efficacy endpoints collected as part of the OCT assessments, and are measured in mm:

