## 8.12 Efficacy Assessments

Efficacy assessments include BCVA, mobility course, FST, OCI, PROs, PLR, and NIRAF.

If possible, photoreceptor outer segment layer thickness will be calculated from OCT images as a secondary efficacy parameter. This assessment will be conducted for those subjects for whom high quality imaging to evaluate this parameter can be obtained, as determined by the Investigator.

Subjects' assessment of the impact of their visual disability on general health-related outcomes as well as specific vision-related outcomes of daily living will be assessed for adult subjects by the VFQ-25 and for pediatric subjects by the CVAQC.

Secondary efficacy response criteria will be obtained as indicated per the SOE

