### 4.7.6. Optical Coherence Tomograph (OCT)

Optical coherence tomography (OCT) will measure full retinal thickness (FRT), outer nuclear layer (ONL) thickness, presence of macular edema, and photoreceptor outer segment layer thickness (PROST) performed by an independent reading center according to the schedule of events (Section 2.4). The OCT values will be summarized by treatment group, eye and visit for the Safety Population using continuous descriptive statistics or categorical descriptive statistics. OCT data and any comments that may be relevant to the OCT grading will be listed for each subject in the Safety Population. The measures listed

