## Statistical Analysis Plan Template

Sponsor:	ProQR Therapeutics		
Protocol:	PQ-110-002		
Document Version No.:	1.0	Document Date:	04 JAN 2022

below, regardless of confidence score (high confidence, adequate confidence, inadequate confidence) will be used for summaries and listings.

The following categorical data are collected as part of the OCT assessments:

- Confidence Score
- Confidence Score Reason
- Presence of Cystoid Macular Edema
- Additional Retina Morphology on Any Scan:
- Vitreous Debris/Cells
- Epiretinal Membrane
- Normal Retina/Fovea Contour
- Retinal Striae
- Foveal Distortion
- Adverse event of special interest (AESI) parameters

- Final AESI determination
- AESI comments OCT related comments

The following continuous data are collected as part of the OCT assessments, and are measured in mm:

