## Statistical Analysis Plan Template

Sponsor:	ProQR Therapeutics		
Protocol:	PQ-110-002		
Document Version No.:	1.0	Document Date:	04 JAN 2022

Section 2.4 and the Imaging Charter. For oculomotor instability assessments with and without fixation, confidence score will be listed and summarized using descriptive statistics for categorical data, and comments that may be relevant to the grading will be listed.

The following continuous data are collected as part of the oculomotor instability assessments (with and without fixation), and summarized using continuous descriptive statistics for the Efficacy Evaluable

Population:

- Mean Gaze Shift
- Oculomotor Instability
- Overall Oculomotor Instability Measurement
- Excluded Frames Count
- Calculated Frames Count

All measures, regardless of confidence score (high confidence, adequate confidence, inadequate confidence) will be summarized by treatment group, fixation (with or without), eye and visit, and listed. In addition, tables with individual values over time will also be produced, for both original and change from baseline values.

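### OCT and oculomotor summaries include readings graded inadequate, with no version that leaves them out, and the protocol's image-quality limit on outer-segment thickness is not carried into the SAP

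*SAP*

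**What the plan says.** **OCT as efficacy (SAP 4.8.4).** This section covers parameters of the EZ line and width. It plans the main descriptive table: "These OCT values will be summarized by treatment group, eye and visit for the Efficacy Evaluable Population using continuous descriptive statistics". The measures, "regardless of confidence score (high confidence, adequate confidence, inadequate confidence) will be used for summaries and listings".

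**OCT as safety (SAP 4.7.6).** This section names "photoreceptor outer segment layer thickness (PROST) performed by an independent reading center" and repeats the rule for the measures it lists: "below, regardless of confidence score (high confidence, adequate confidence, inadequate confidence) will be used for summaries and listings".

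**Oculomotor instability (SAP 4.8.6).** "All measures, regardless of confidence score (high confidence, adequate confidence, inadequate confidence) will be summarized by treatment group", and also by fixation condition, eye and visit.

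**Protocol 8.12.** Outer-segment thickness, a secondary efficacy parameter, is to be calculated where possible, and only "for those subjects for whom high quality imaging to evaluate this parameter can be obtained, as determined by the Investigator".

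**SAP Section 5.** The list of changes drops the exploratory EZ endpoint because it is taken to be the same as the secondary OCT endpoint, and refers to 4.8.4. It does not mention image quality.

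**FST (SAP 4.8.3), for comparison.** "Descriptive statistics will be based on only successful thresholds"; failed thresholds appear only in a listing.

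**The concern.** The SAP collects a confidence score and then does not use it to decide which measurements enter a mean. A value graded inadequate counts the same as one graded high, and no table shows whether the result depends on such values. For outer-segment thickness the protocol had set an image-quality condition. SAP 1.2 undertakes to outline differences from the protocol, but the SAP does not say how this condition is met or whether it has been dropped.

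Poor readings are plausible in this disease. Protocol 2.1 lists sensory nystagmus among its signs, and Protocol 8.12 itself treats the thickness measure as not always obtainable. Quality control may also differ between baseline and follow-up. Protocol 4.2.1.1 allows a pre-dose assessment to be repeated if its quality is unacceptable. No matching rule is stated for later visits, although the Investigator may order extra evaluations.

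At stake is how far the secondary structural and oculomotor results can be interpreted. Each mean and its 95% confidence interval rest on very few eyes.

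**Working it through.** The plan gives no figure on this point to reproduce. The check is a comparison of the texts, followed by a simple measure of scale.

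**1. Which rule reaches outer-segment thickness?** It is named in SAP 4.7.6, which uses all grades. If it is instead handled through the EZ measures, as Section 5 suggests, SAP 4.8.4 applies, which also uses all grades. The lists of continuous measures in both sections are not visible in the public copy. The conclusion does not depend on them, because the rule is the same either way.

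**2. Do the protocol limit and the SAP rule concern the same thing?**

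| | Protocol 8.12 | SAP 4.7.6 and 4.8.4 |
|---|---|---|
| Unit | Subject | Reading |
| Who judges | Investigator | Confidence score in the reading-centre data |
| Effect | Decides whether thickness is assessed | Inadequate grade does not remove a value |
| Scope | Outer-segment thickness only | OCT measures (OCI has its own rule in 4.8.6) |

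The two could operate in sequence: the Investigator decides who can be assessed, and every reading from those subjects is then summarised. The SAP does not say so, and it contains no subject-level quality condition.

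**3. Do other provisions remove inadequate readings from the means?**
- SAP 4.7.6 counts as missing the OCT values that could not be graded or were not applicable. An inadequate reading that still has a number is in neither category.
- The Per Protocol set (SAP 3.1) can drop data points, but only for major protocol deviations. A low confidence grade is not stated to be one.
- Individual-value tables (SAP 4.8.4, 4.8.6) and listings show the data but leave the mean and interval unchanged.

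**4. Scale.** Inputs: at most 11 subjects (Protocol 5.1), and an assumed 4 to 6 per dose group, since group sizes are not given. One reading wrong by d moves a group mean by d/n:
- n = 11: d/11 = 0.09d
- n = 6: d/6 = 0.17d
- n = 4: d/4 = 0.25d

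If the faulty reading is the baseline, the mean change at every visit to which that subject contributes moves by the same amount in the opposite direction.

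**5. Does including the inadequate readings widen the standard error?** Let f be the share of inadequate readings, k the ratio of their measurement SD to that of the others, and s the share of total variance due to measurement error among the other readings. All three are assumptions, and readings are taken as independent and unbiased. The variance of the mean is proportional to [1 + f·s·(k² − 1)]/n with all readings and to 1/[(1 − f)n] without the inadequate ones. So

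SE ratio (all ÷ restricted) = √[(1 − f)(1 + f·s·(k² − 1))].

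- f = 0.2, k = 2, s = 1: √(0.8 × 1.6) = 1.13
- f = 0.3, k = 3, s = 1: √(0.7 × 3.4) = 1.54
- f = 0.2, k = 2, s = 0.2: √(0.8 × 1.12) = 0.95

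Inclusion narrows the standard error whenever s < 1/[(1 − f)(k² − 1)]. For f = 0.2 and k = 2 that threshold is 1/(0.8 × 3) = 0.42; for f = 0.3 and k = 3 it is 1/(0.7 × 8) = 0.18. Even the direction depends on s, which the documents do not give.

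**The case against.** **No protocol conflict.** The protocol limit decides who is assessed and the confidence score describes a reading, so both can be honoured. This stands. A reader might infer that the SAP contradicts Protocol 8.12, or that Section 5 omits a proven change. The documents show only that the two texts are not reconciled. The limit does not reach OCI at all.

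**The FST rule is not a true precedent.** FST drops tests that failed. The closer OCT counterpart is an ungradable image, which SAP 4.7.6 already treats as missing. This also stands: FST shows that quality filters exist elsewhere in the SAP, not that the SAP is inconsistent.

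**Precision may not suffer.** A reader might infer that pooling poor readings must widen the intervals. Step 5 shows that this cannot be claimed. With few eyes the t multiplier also matters. Going from 5 eyes to 4 raises it from 2.776 to 3.182, so at f = 0.2, k = 2, s = 1 the ratio of 95% interval widths is 1.13 × 2.776/3.182 = 0.99.

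**Exclusion has its own bias.** If unstable eyes give poorer readings, which is plausible but not documented, dropping them selects steadier eyes. For OCI that may mean selecting on the outcome. Using all readings as the main OCI analysis is therefore defensible.

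**Much is already visible.** OCI confidence scores are summarised alongside counts of excluded and calculated frames, OCT scores are collected, and individual values are tabulated. In so small a study this helps a reader. It does not provide a summary without the inadequate readings or say how the protocol's limit is applied.

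**Conclusion.** The point holds as a modest gap that is cheap to close. Three SAP sections put inadequate-confidence readings into the summaries, and no summary without them is planned. For outer-segment thickness, and for the EZ measures that Section 5 equates with the same secondary endpoint, the SAP neither applies nor reconciles the protocol's image-quality limit. For OCI the issue is analysis quality alone.

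The supportable size is the influence of a single reading: 0.09d at the maximum of 11 subjects, or 0.17d to 0.25d at an assumed 4 to 6 per group. No percentage change in standard error can be supported, because the share of inadequate readings, their error and the variance split are all unknown. What the grade means in practice may be set out in reading-centre documents not available here. The endpoints are secondary and descriptive, so no error rate, power figure or primary endpoint is affected.

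**What to change.** - **SAP 4.7.6 and 4.8.4:** state how the limit in Protocol 8.12 is applied to the outer-segment and EZ summary, and apply it; otherwise record the departure in Section 5. Show this table both with and without inadequate-confidence readings.
- **SAP 4.8.6:** keep all readings in the main OCI table and add a sensitivity table restricted to high and adequate confidence.
- **All restricted tables:** say whether a change from baseline is dropped when either of its two readings is inadequate. Report the number of excluded readings by eye and visit, and keep every reading in the listings.

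The confidence scores are already collected, so the cost is SAP wording and a few tables. The restricted versions will have fewer data points and may favour eyes with steadier fixation, which is why both versions should be shown.

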## Statistical Analysis Plan Template

Sponsor:	ProQR Therapeutics		
Protocol:	PQ-110-002		
Document Version No.:	1.0	Document Date:	04 JAN 2022

-A second table with individual observed values and change from baseline over time will also be produced. Subject level listings will also be produced for OCT.

### 4.8.5. **NIRAF**

The following categorical data are collected as part of the NIRAF assessments performed by an independent reading center according to the schedule of events in Section 2.4 and the Imaging Charter:

- Confidence Score
- Confidence Score Reason

The following continuous data are collected as part of the NIRAF assessments, and summarized using continuous descriptive statistics by treatment group, eye and visit for the Efficacy Evaluable Population:

- Horizontal Diameter of Retained Central Hyperautofluorescent Island (mm)
- Vertical Diameter of Retained Central Hyperautofluorescent Island (mm)
- Area of Retained Central Hyperautofluorescent Island (mm)

Confidence score will be listed and summarized using descriptive statistics for categorical data by treatment group, eye and visit, and confidence score reason will be listed only.

Tables with individual values over time will be produced, for both original and change from baseline values. Subject level listings will also be produced for NIRAF.

### 4.8.6. **Oculomotor Instability**

A confidence score is collected for each eye as part of the oculomotor instability assessments (with and without fixation) performed by an independent reading center according to the Schedule of Events of

## Statistical Analysis Plan Template

Sponsor:	ProQR Therapeutics		
Protocol:	PQ-110-002		
Document Version No.:	1.0	Document Date:	04 JAN 2022

Section 2.4 and the Imaging Charter. For oculomotor instability assessments with and without fixation, confidence score will be listed and summarized using descriptive statistics for categorical data, and comments that may be relevant to the grading will be listed.

The following continuous data are collected as part of the oculomotor instability assessments (with and without fixation), and summarized using continuous descriptive statistics for the Efficacy Evaluable

Population:

- Mean Gaze Shift
- Oculomotor Instability
- Overall Oculomotor Instability Measurement
- Excluded Frames Count
- Calculated Frames Count

All measures, regardless of confidence score (high confidence, adequate confidence, inadequate confidence) will be summarized by treatment group, fixation (with or without), eye and visit, and listed. In addition, tables with individual values over time will also be produced, for both original and change from baseline values.

### 4.8.7. Pupillary Light Reflex

PLR imaging measures pupil size with various candela per square meter stimuli (ie, at 4, 40, 400 and 4000 cd/m^2); it is used to test integrity of the sensory and motor functions of the eye. For PLR amplitude parameters, higher values are indicative of better status. For PLR latency parameters, lower values are indicative of better status.

The mean observed value and change from baseline values for the following parameters will be summarized for the different stimuli (ie, at 4, 40, 400 and 4000 cd/m^2) by treatment group, eye and visit for the Efficacy Evaluable Population using descriptive statistics:

- pre-stimulus (mm)

## Statistical Analysis Plan Template

Sponsor:	ProQR Therapeutics		
Protocol:	PQ-110-002		
Document Version No.:	1.0	Document Date:	04 JAN 2022

- maximum amplitude (mm)
- 0.9 seconds amplitude (mm)
- Latency (s)

In addition, the following derived parameter will be summarized as well: maximum amplitude minus pre-stimulus at 4000 cd/m^2

Subject level listings will also be produced for PLR.

### 4.8.8. VFQ-25/CVAQC

The observed value and change from baseline values over time for overall VFQ-25 composite scores for adult subjects and CVAQC scores for pediatric subjects will be summarized by treatment group and visit for the Efficacy Evaluable Population and Per Protocol Analysis Set using descriptive statistics. Descriptive summaries of VFQ-25/CVAQC for the subpopulations of subjects defined in Section 4.2.7 will also be provided. Subject level listings will be produced.

- **VFQ-25** Scoring VFQ-25 is a two-step process:

**Step 1:** original numeric values from the survey are re-coded following the scoring rules outlined in Table 6. All items are scored so that a high score represents better functioning. Each item is then converted to a 0 to 100 scale so that the lowest and highest possible scores are set at 0 and 100 points, respectively. In this format scores represent the achieved percentage of the total possible score, e.g. a score of 50 represents 50% of the highest possible score.

**Step 2:** items within each sub-scale are averaged together to create the 12 subscale scores. Table 7 indicates which items contribute to each specific sub-scale. Items that are left blank (missing data) are not taken into account when calculating the scale scores. Sub-scales with at least one item answered can be used to generate a sub-scale score. Hence, scores represent the average for all items in the subscale that the respondent answered.

